### **11.3 Participant Replacement**

Participants who withdraw or are withdrawn will be replaced until the desired sample size is reached.

### **11.4 Follow-up after Early Study Withdrawal**

Participants who withdraw from the study after receiving dose 1 will be followed as described in Section 6.5 Premature Discontinuation of Investigational Agent.

### **11.5 Study Stopping Rules**

Study enrollment and treatment will be suspended pending expedited review of all pertinent data after the occurrence of:

1. 1 death regardless of relationship to the investigational agent
2. 1 anaphylactic reaction grade 3 (see Section 12.3.2, Grading Criteria for Anaphylaxis) possibly related to the investigational agent
3. Either of the following events, which are considered related to the study procedures or treatments, in at least 2 participants:
  - a. Anaphylactic reaction grade 2 (see Section 12.3.2, Grading Criteria for Anaphylaxis).
  - b. Hypotensive shock: Drop in blood pressure: Systolic < 90 mm Hg or < 80% of baseline, whichever is higher, and diastolic blood pressure < 60 mm Hg-absolute.

If the study is stopped due to meeting the above criteria, it may not be resumed until all pertinent information is discussed with DAIT NIAID, NIAID Asthma and Allergy DSMB, and the site IRBs, and all parties concur with the resumption of the study.

The study may be terminated by DAIT/NIAID or the NIAID DSMB upon review of any observations, events, or new information that merit such action.

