Study Stopping Rules	
Study enrollment and treatment will be suspended pending expedited review of all pertinent data after the occurrence of:
 

1) 1 death regardless of relationship to the investigational agent

2) 1 anaphylactic reaction grade 3 possibly related to the investigational agent

3) Either of the following events, if considered related to the study procedures or treatments, in at least 2 participants:

a) Anaphylactic reaction grade 2.

b) Hypotensive shock: Drop in blood pressure: Systolic < 90 mm Hg or < 80% of baseline, whichever is higher, and diastolic blood pressure < 60 mm Hg-absolute.

----------------------	--

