## **8.2 Screening/Baseline Visit**

This research study will be explained in lay terms to each potential research participant. The potential participant will provide informed consent before he or she undergoes any screening study procedures. Written informed consent and Health Insurance Portability and Accountability Act (HIPAA) authorization will be obtained from all participants at the beginning of this visit. Study procedures will be stopped and the participant will be deemed ineligible for the study at any point during the Screening Visit if and when they fail to meet eligibility criteria.

After the consent is signed, participants will undergo screening study procedures, including prick skin tests with mouse allergenic extract to ensure participants are sensitive to the test product, since those who do not react to mouse are excluded from the remainder of the study. In addition, participants will be tested with: American cockroach, German

cockroach, cat, dog, Alternaria, house dust mite, and selected seasonal aeroallergen allergenic extracts, as specified in the study MOP, to characterize the study population.

A medical history will be taken and a targeted physical examination will be performed to verify the participant's suitability for inclusion in the study. A urine pregnancy test will also be performed on all female participants.

Spirometry will be performed by all participants to verify the participant's suitability for inclusion in the study. Candidates whose FEV1 is less than 70% of predicted normal will be excluded; however, if their asthma can be brought under control within 2 months, as described in Section 8.3, they are eligible for rescreening.

Blood will be collected by venipuncture for mouse-specific IgE antibody testing.

Participants must agree to receive a flu vaccine if they are in the study during flu season. Participants will be offered a flu vaccine when it becomes available. Participants may choose to receive the flu vaccine outside of the study.

Participants who have both a positive skin prick test to mouse allergenic extract and a mouse-specific IgE  $\geq 0.10$  kU/L and are considered eligible for the study, and at the discretion of the study clinician, will be invited to proceed to the Dose Initiation Visit.

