**Study mandated procedures:**

**Allergen Scratch Skin Testing**

- Prolonged (>24 hours) itching at test site
- Swelling (> 10 cm ) at site of test lasting more than 24 hours

- Nasal allergic symptoms within 30 minutes of the procedure
- Fainting/Vasovagal event within 30 minutes of the procedure
- Anaphylaxis

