**Table 12.3.2 Grading System of Severity of Anaphylaxis**

Grade	Defined By
1. Mild (skin & subcutaneous tissues, GI, &/or mild respiratory)	Flushing, urticaria, periorbital or facial angioedema; mild dyspnea, wheeze or upper respiratory symptoms; mild abdominal pain and/or emesis
2. Moderate (mild symptoms + features suggesting moderate respiratory, cardiovascular or GI symptoms)	Marked dysphagia, hoarseness, and/or stridor; SOB, wheezing & retractions; crampy abdominal pain, recurrent vomiting and/or diarrhea; and/or mild dizziness
3. Severe (hypoxia, hypotension, or neurological compromise)	Cyanosis or SpO 2 < 92% at any stage, hypotension, confusion, collapse, loss of consciousness; or incontinence

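### Stopping rule 3a counts a procedure-related grade 2 anaphylactic reaction but not a grade 3 reaction to the same procedure

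*Combined protocol and SAP*

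**What the plan says.** The rules that suspend enrollment and treatment are in section 11.5 and, in near-identical words, in the Protocol Synopsis.

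- Item 1 covers any death.
- Item 2 covers "1 anaphylactic reaction grade 3 (see Section 12.3.2, Grading Criteria for Anaphylaxis) possibly related to the investigational agent". Study procedures are not named.
- Item 3 has wider attribution and a higher count: "Either of the following events, which are considered related to the study procedures or treatments, in at least 2 participants".
- Item 3a is "Anaphylactic reaction grade 2 (see Section 12.3.2, Grading Criteria for Anaphylaxis"); the synopsis has "Anaphylactic reaction grade 2".
- Item 3b is hypotensive shock: "Systolic < 90 mm Hg or < 80% of baseline, whichever is higher, and diastolic blood pressure < 60 mm Hg-absolute".

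Table 12.3.2 makes a reaction grade 3 for cyanosis or oxygen saturation below 92%, and also for "hypotension, confusion, collapse, loss of consciousness; or incontinence". Any one of these is enough.

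Section 12.2.1 lists the related events for each study procedure. Anaphylaxis appears under "Allergen Scratch Skin Testing" but not under blood draws or pulmonary function testing. Screening is not limited to the mouse prick. Section 8.2 says "In addition, participants will be tested with: American cockroach", and goes on to German cockroach, cat, dog, Alternaria, dust mite and seasonal extracts.

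**The concern.** A safety trigger should not ignore the more severe form of an event that it counts. Item 2 covers grade 3 but only for the extract. Item 3a covers procedures but only for grade 2. A grade 3 reaction due solely to a procedure falls between them unless it meets 3b. For that case the rule is not monotone in severity: two participants with a grade 2 reaction to a skin prick suspend the study, while two with a grade 3 reaction to the same prick need not.

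Only the automatic, study-level suspension is at stake. The care of the affected person and the reporting of the event do not depend on it.

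**Working it through.** No figure in the plan depends on this point. The check applies each item literally to the same event.

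**Step 1. Isolate the case.** Take a reaction that is non-fatal, grade 3, attributed only to a procedure, and outside the 3b limits.

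- Item 1: no death, so not met.
- Item 2: not possibly related to the extract, so not met.
- Item 3a: grade 3 is not grade 2, so not met.
- Item 3b: needs the systolic and the diastolic limit together. Low saturation, confusion or collapse makes a reaction grade 3 without either, so not met.

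**Step 2. Is 'grade 2' shorthand for 'at least grade 2'?** The protocol's usage elsewhere is against it. The exclusion on past anaphylaxis in section 4.3 says grade 2 or higher, and section 11.2 item 2 says grade 2 or 3. Where grade 3 is meant, it is written.

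**Step 3. Run event patterns through the rule.** Unless stated otherwise, every event is non-fatal, procedure-only and outside 3b. Each row with more than one event involves different participants.

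| Pattern | As written | 3a as 'grade 2 or higher' |
|---|---|---|
| One grade 2 | none | none |
| Two grade 2 | 3a | 3a |
| One grade 3 | none | none |
| Two grade 3 | none | 3a |
| Ten grade 3 | none | 3a |
| One grade 2 and one grade 3 | none | 3a |
| One grade 3, possibly related to the extract | item 2 | item 2 |

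After one procedure-only grade 3 reaction, the number of further participants with grade 2 needed for 3a is 2 − 0 = 2 as written and 2 − 1 = 1 with the change.

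**Step 4. Where could it arise?** Skin testing is the only procedure listed with anaphylaxis. Appendix A places it at screening only; section 7.3 also mentions skin testing at the final visit. The mouse prick uses the treatment extract (section 4.2, item 3), so item 2 can fire if that prick cannot be ruled out as a possible cause. The clear case is a non-mouse prick. Adverse events are collected from consent (section 12.4), so a screening reaction is a recorded event, even though Appendix A leaves the adverse event row blank at screening.

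**Step 5. Does the change affect anything else?** Section 11.5 allows resumption after a suspension. Suppose one extract-related grade 3 reaction has fired item 2, the study has resumed, and earlier events stay in the count (the protocol does not say). As written, 3a then needs 2 − 0 = 2 participants with grade 2. With 'grade 2 or higher' it needs 2 − 1 = 1 other participant. The overlap between items 2 and 3a is therefore not neutral, although the change is conservative.

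**The case against.** The strongest case against acting has three parts.

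First, the case is nearly empty. Four conditions must coincide. Section 8.2 puts the mouse and non-mouse pricks in one visit, and anyone eligible has reacted to the mouse prick. Table 12.3.3 defines a possible relationship as a reasonable possibility with some evidence of cause. Ruling out the study extract would often be hard, and item 2 would then fire. This stands, and it limits the weight of the point.

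Second, a severe reaction to a cat or cockroach prick before any dose says little about mouse immunotherapy, so tying the single-event trigger to the extract is reasonable. That defends item 2, which should stay as it is. It does not defend 3a, which already counts a grade 2 reaction to the same prick.

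Third, other safeguards apply. Section 11.2 withdraws the person for grade 2 or 3 whatever the cause. SAEs reach DAIT/NIAID within 24 hours regardless of relationship (12.5.1). The DSMB receives SAE listings on an ongoing basis (12.8.2), and immediately for an SAE judged an unexpected risk (12.8.2.1). An ad hoc review can be requested and halts enrollment and dosing (12.8.2.2, 12.8.2.3), and DAIT/NIAID or the DSMB may terminate the study (11.5). A reader might infer from the gap that a severe reaction could pass unnoticed or that treatment would continue unexamined. The documents do not support that. What remains is that each study-level route depends on a judgement or a request, whereas a stopping rule exists to make suspension automatic.

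**Conclusion.** The gap is real on the wording of both section 11.5 and the synopsis, but it is narrow: a non-fatal, procedure-only grade 3 reaction outside the 3b limits, in practice to a non-mouse skin prick at screening.

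Its frequency cannot be sized. The documents give no rate for such reactions. The people at risk are those screened, whose number is not stated, rather than the 10 to 12 treated, so a calculation on the treated number would use the wrong base. The event should be rare. The change is worth making for coherence of the automatic trigger, not for a measurable gain in the chance of suspension.

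Three stronger readings are not supported. Extract-related grade 3 reactions do not escape, because one is enough under item 2. One procedure-related grade 2 reaction does not suspend the study, because 3a needs two participants. The change would not make one procedure-only grade 3 reaction suspend the study; it would only count towards the two.

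The conclusion rests on reading 3a literally and on counting a person who reacts at screening as a participant, which is how section 8.2 uses the word.

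**What to change.** In section 11.5 item 3a and synopsis item 3a, write 'Anaphylactic reaction grade 2 or higher'. Leave item 2 unchanged, so that one extract-related grade 3 reaction still suspends the study.

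State the side effect with the change: after resumption from an item 2 suspension, the earlier reaction would count in 3a, and one grade 2 reaction in another participant would suspend the study again. If that is not wanted, write 'grade 2, or grade 3 not already counted under item 2', which keeps the present count of two after resumption.

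The cost is a few words in two places. No trigger is removed, and no procedure, data collection or analysis changes. Local IRB approval is needed as for any amendment (section 16.1), so the edit can wait for the next one.

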## 12 Safety Monitoring and Reporting

### 12.1 Overview

This section defines the types of safety data that will be collected under this protocol and outlines the procedures for appropriately collecting, grading, recording, and reporting those data. Adverse events that are classified as serious according to the definition of the FDA must be reported promptly (per Section 12.5, Reporting of Serious Adverse Events and Adverse Events) to DAIT/NIAID. Appropriate notifications will also be made to site principal investigators, and to the Institutional Review Boards (IRBs).

Information in this section complies with ICH Guideline E2A: Clinical Safety Data Management: Definitions and Standards for Expedited Reporting, ICH Guideline E-6: Guideline for Good Clinical Practice, 21CFR Parts 312 and 320, and applies the standards set forth in the National Cancer Institute (NCI), Common Terminology Criteria for Adverse Events (CTCAE), Version 4.03, June 14, 2010: <http://ctep.cancer.gov/reporting/ctc.html>.

### 12.2 Definitions

#### 12.2.1 Adverse Event (AE)

An adverse event is any untoward or unfavorable medical occurrence associated with the subject's participation in the research, whether or not considered related to the subject's participation in the research (modified from the definition of adverse events in the 1996 International Conference on Harmonization E-6 Guidelines for Good Clinical Practice) (from OHRP "Guidance on Reviewing and Reporting Unanticipated Problems Involving Risks to Subjects or Others and Adverse Events (1/15/07)" (<http://www.hhs.gov/ohrp/policy/advevntguid.html#Q2>)

For this study, a related adverse events will include any untoward or unfavorable medical occurrence associated with:

**Study therapy regimen:** Mouse Allergenic Extract Administered by the Subcutaneous Route

- Eye symptoms (itchy, runny, swelling)
- Nose symptoms (sneezing, itching, runny, stuffy)
- Mouth/ears/throat symptoms (itchy mouth, throat irritation, oral or throat angioedema, cough, itchy ears)
- Skin symptoms (angioedema, urticaria, generalized itching, rash)
- Gastrointestinal symptoms (vomiting, diarrhea, cramps, nausea)
- Chest (cough, tightness, wheezing)
- Anaphylaxis
- Injection site reaction  $\geq 6$  cm in diameter

**Study mandated procedures:**

**Allergen Scratch Skin Testing**

- Prolonged (>24 hours) itching at test site
- Swelling (> 10 cm ) at site of test lasting more than 24 hours

- Nasal allergic symptoms within 30 minutes of the procedure
- Fainting/Vasovagal event within 30 minutes of the procedure
- Anaphylaxis

### **Blood Draws**

- Fainting/Vasovagal events
- Bruising at puncture site larger than 2 cm diameter
- Bleeding from puncture site lasting more than 30 minutes
- Swelling at puncture site larger than 2 cm

### **Pulmonary Function Testing**

- Wheezing or bronchoconstriction requiring treatment with bronchodilators within 30 minutes from the procedure
- Coughing requiring treatment with bronchodilators within 30 minutes from the procedure

#### **12.2.2 Suspected Adverse Reaction (SAR)**

Suspected adverse reaction (SAR) means any adverse event for which there is a reasonable possibility that the investigational study therapy regimen caused the adverse event. For the purposes of safety reporting, 'reasonable possibility' means there is evidence to suggest a causal relationship between the drug and the adverse event. A suspected adverse reaction implies a lesser degree of certainty about causality than adverse reaction, which means any adverse event caused by a drug (21 CFR 312.32(a)).

#### **12.2.3 Unexpected Adverse Event**

An adverse event or suspected adverse reaction is considered "unexpected" if it is not listed in the safety information of Greer's package insert for allergenic extracts or is not listed at the specificity, severity or rate of occurrence that has been observed; or is not consistent with the risk information described in the protocol.

"Unexpected" also refers to adverse events or suspected adverse reactions that are mentioned in the package insert as occurring with a class of drugs or as anticipated from the pharmacological properties of the drug, but are not specifically mentioned as occurring with the particular drug under investigation (21 CFR 312.32(a)).

#### **12.2.4 Serious Adverse Event (SAE)**

An adverse event or suspected adverse reaction is considered "serious" if, in the view of either the investigator or DAIT/NIAID, it results in any of the following outcomes (21 CFR 312.32(a)):

1. Death: A death that occurs during the study or that comes to the attention of the investigator during the protocol-defined follow-up period must be reported whether it is considered treatment related or not.
2. A life-threatening event: An AE or SAR is considered "life-threatening" if, in the view of either the investigator or DAIT/NIAID, its occurrence places the subject at immediate risk of death. It does not include an AE or SAR that, had it occurred in a more severe form, might have caused death.
3. Inpatient hospitalization or prolongation of existing hospitalization.
4. Persistent or significant incapacity or substantial disruption of the ability to conduct normal life functions.
5. Congenital anomaly or birth defect.

6. Important medical events that may not result in death, be life threatening, or require hospitalization may be considered serious when, based upon appropriate medical judgment, they may jeopardize the subject and may require medical or surgical intervention to prevent one of the outcomes listed above.

Elective hospitalizations or hospital admissions for the purpose of conduct of protocol mandated procedures are not to be reported as an SAE unless hospitalization is prolonged due to complications.

### **12.3 Grading and Attribution of Adverse Events**

#### **12.3.1 Grading Criteria**

The study site will grade the severity of adverse events experienced by the study subjects according to the criteria set forth in the National Cancer Institute's Common Terminology Criteria for Adverse Events (CTCAE) (Version 4.03, June 14, 2010). This document (referred to herein as the NCI-CTCAE manual) provides a common language to describe levels of severity, to analyze and interpret data, and to articulate the clinical significance of all adverse events. The NCI-CTCAE has been reviewed by the Protocol Chair and has been deemed appropriate for the subject population to be studied in this protocol.

Adverse events will be graded on a scale from 1 to 5 according to the following standards in the NCI-CTCAE manual:

Grade 1 = mild adverse event.

Grade 2 = moderate adverse event.

Grade 3 = severe and undesirable adverse event.

Grade 4 = life-threatening or disabling adverse event.

Grade 5 = death.

For grading an abnormal value or result of a clinical or laboratory evaluation (including, but not limited to, a radiograph, an ultrasound, an electrocardiogram etc.), a treatment-emergent adverse event is defined as an increase in grade from baseline or from the last post-baseline value that doesn't meet grading criteria. Changes in grade from screening to baseline will also be recorded as adverse events, but are not treatment-emergent. If a specific event or result from a given clinical or laboratory evaluation is not included in the NCI-CTCAE manual, then an abnormal result would be considered an adverse event if changes in therapy or monitoring are implemented as a result of the event/result.

#### **12.3.2 Grading Criteria for Anaphylaxis**

This study will grade anaphylaxis as defined by the following table, adapted from the grading scale of [name].

**Table 12.3.2 Grading System of Severity of Anaphylaxis**

Grade	Defined By
1. Mild (skin & subcutaneous tissues, GI, &/or mild respiratory)	Flushing, urticaria, periorbital or facial angioedema; mild dyspnea, wheeze or upper respiratory symptoms; mild abdominal pain and/or emesis
2. Moderate (mild symptoms + features suggesting moderate respiratory, cardiovascular or GI symptoms)	Marked dysphagia, hoarseness, and/or stridor; SOB, wheezing & retractions; crampy abdominal pain, recurrent vomiting and/or diarrhea; and/or mild dizziness
3. Severe (hypoxia, hypotension, or neurological compromise)	Cyanosis or SpO 2 < 92% at any stage, hypotension, confusion, collapse, loss of consciousness; or incontinence

**12.3.3 Attribution Definitions**

The relationship, or attribution, of an adverse event to study procedure(s) will initially be determined by the site investigator and recorded on the appropriate AE/SAE paper case report form. Final determination of attribution for safety reporting will be determined by DAIT/NIAID. The relationship of an adverse event to study procedures will be determined using the descriptors and definitions provided in Table 12.3.3.

For additional information and a printable version of the NCI-CTCAE manual, consult the NCI-CTCAE web site: <http://ctep.cancer.gov/reporting/ctc.html>.

**Table 12.3.3 Attribution of Adverse Events**

Code	Descriptor	Relationship (to primary investigational product and/or other concurrent mandated study therapy or study procedure)
Unrelated Category		
1	Unrelated	The adverse event is clearly not related.
Related Categories		
2	Possible	The adverse event has a reasonable possibility to be related; there is evidence to suggest a causal relationship.
3	Definite	The adverse event is clearly related.

**12.4 Collection and Recording of Adverse Events**

Adverse events (including SAEs) will be collected from the time of consent until a subject completes study participation or until 30 days after he/she prematurely withdraws (without withdrawing consent) or is withdrawn from the study.

**12.4.1 Collecting Adverse Events**

Adverse events (including SAEs) may be discovered through any of these methods:

- Observing the participant.

- Interviewing the participant.
- Receiving an unsolicited complaint from the participant.
- In addition, an abnormal value or result from a clinical or laboratory evaluation can also indicate an adverse event, as defined in Section 12.3, Grading and Attribution of Adverse Events.

